14.3 Data Handling

14.3.1 Measurement Times

14.3.1.1 Visit Windows

Visit windows will not be used. The nominal visit time point entered on the case report forms will be used. Unscheduled assessments, if any, will be listed, but will not be included in tabulations by visit.

14.3.1.2 Baseline Values

All assessments on Day 1, before the first dose of the study drug, will be considered as Baseline. If the value at Baseline is missing, the last value from the Screening visit will be used as Baseline. If there are multiple Baseline assessments, the most recent one will be used for analysis.

14.3.2 Missing Data Conventions

Unless otherwise specified, missing data will be considered missing at random and will not be imputed. However, imputation of partial dates may be performed during the data analysis and will be documented.

14.4 Statistical Methods

14.4.1 General Overview and Plan of Analysis

Summary statistics will be presented to describe the analysis populations, namely, the ITT, SE, and CS populations. Tabulations will include the number of subjects, mean, standard deviation, minimum, median, and maximum for continuous variables; and/or frequency and percentage of subjects for categorical variables. Summary statistics for certain safety parameters will also be presented for the MTD population.

For all subjects, the data will be tabulated by dose cohort and for the total patient population.

All statistical analyses will be performed using SAS version 9.1 (or higher), unless specified otherwise. The use of other statistical software will not be considered a violation of the statistical analysis plan, nor require an amendment of this plan.

Version 5

14.4.2 Hypothesis Testing

There is no formal hypothesis testing in this study.

14.4.3 Interim Analysis

There is no planned interim analysis in this study, unless periodic reports are requested by the Sponsor before the trial begins.

14.5 Statistical Analysis

14.5.1 Disposition of Subjects

The analyses of subject disposition will be performed on the ITT population. The number and percentage of subjects will be presented by number of cycles of study drug completed. The number of subjects who completed follow-up and those who terminated early from treatment or the study, along with their reasons for early termination, will be presented. Reasons for termination from the study are described in the protocol.

14.5.2 Baseline Characteristics

14.5.2.1 Demographic Characteristics

Summary statistics for demographic characteristics will be presented for the ITT population (or SE population, if all subjects received the study drug). Tabulations for age, sex, ethnicity, and race will be presented. Age (years) will be calculated as the integer part of ((date of screening – date of birth + 1)/365.25).

14.5.2.2 Physical Characteristics

Summary statistics will be presented for height (cm), weight (kg), and BMI at Screening for the ITT population.

14.5.2.3 Clinical Status

Summary statistics for the following measures of clinical status will be presented for the ITT population.

- Multiple Sclerosis Functional Composite (MSFC) score
- Fatigue Severity Scale (FSS) score
- Short Form Health Survey (SF-36) score
- Expanded Disability Status Scale (EDSS) score
- MRI findings

• Self-reported and clinically confirmed clinical exacerbations

14.5.3 Analysis of Safety and Tolerability

The analyses of safety endpoints will be conducted on the SE population. Statistical tests will not be performed. The safety profile and MTD of MIS416 will be determined. Adverse events, changes in laboratory measurements, and results of other safety evaluations will be presented. Toxicity rates will be determined.

14.5.3.1 Extent of Exposure

Summary statistics will be presented for the number of infusions and the cumulative drug dose received by subjects in each dose cohort. A corresponding listing will also be generated to show the number of infusions at each dose level, and the total infusions and cumulative drug dose received by each subject.

14.5.3.2 Adverse Events (AE)

"Adverse event" and "adverse experience" may be used interchangeably. All summary tables will be based on coded preferred terms, instead of verbatim terms. All adverse events will be coded, using MedDRA dictionary version 11.0. The use of another version will not be considered a violation of the statistical analysis plan, nor require an amendment to the plan. The categories and definitions of severity and causal relationship for all AEs, including the criteria for which an AE is to be classified as "serious", are as described in the protocol.

The overall incidence of adverse events will be tabulated by dose cohort and total population, including the number and percentage of subjects with at least one: adverse event, serious adverse event, or treatment-related adverse event. The number of deaths and discontinuations due to adverse event(s) will be presented. The incidence of adverse events by intensity/grade (Grades 1, 2, 3, and 4) and by relationship to study drug (not related, possibly related, and probably related), and the incidence of serious adverse events (SAEs) by relationship to study drug, will also be presented. DLTs will be identified in the AE/SAE listings. If there are multiple occurrences of the same AE for the same subject, only the first occurrence will be counted.

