Safety: The primary endpoint is to determine the safety profile and MTD of MIS416. Assessments will include characterization of DLTs; characterization of the type, incidence, severity, timing, seriousness, and relationship to treatment of AEs; effects on vital signs and laboratory parameters; changes in electrocardiograms (ECGs) and ophthalmologic examinations; and safety MRI assessments.

Pharmacodynamics: Pharmacodynamic testing will include some or all of the following serum and cellular assays during the dose-escalation phase: Serum IFN_Y, IL-17, IL-6, TNF α and GM-CSF levels; PBMC expression of mRNA encoding IL-12p40, IL-12p35, IL-23p19, LT α , LT β , IFN_Y, IL-17, GM-CSF, ROR_Yt, and Tbet; PBMC production of IFN_Y, IL-17, and GM-CSF in response to stimulation with anti-CD3 and anti-CD28 ex vivo; PBMC production of IL-12p40, IL-12p70, IL-23, TNF α and IL-6 in response to stimulation with LPS/IFN_Y ex vivo. Depending upon findings during the dose-escalation phase, a more selective or comprehensive set of these assays will be performed during the dose-confirmation phase.

Pharmacogenomic Analysis: Following specific written consent of the subject, at least one aliquot of PBMC will be sent to [name], University of New South Wales, for genomic analysis.

Pharmacokinetics: Pharmacokinetic analysis is not applicable in this study due to the nature of MIS416 and its mode of action.

Clinical Status: Subjects will be assessed by EDSS and Multiple Sclerosis Functional Composite (MSFC)¹⁹; MRIs for clinical status will be performed at the end of the DC phase, according to a protocol to be specified in the Radiology Operations Manual.

Statistical Analysis:

Safety Analyses: Safety data analysis will be conducted on all subjects receiving at least one dose of MIS416. Analyses will consist of data summaries for clinical, biological, and PD parameters, and for AEs. The number and percentage of subjects experiencing one or more AEs will be summarized by dose level group, relationship to study drug, and severity. AEs will be coded using MedDRA terminology. Laboratory parameters will be summarized using descriptive statistics, by post-dosing shifts relative to baseline, and data listings of clinically significant abnormalities. Vital signs, ECG, and ophthalmologic examination data will be summarized by changes from baseline values at each dose

Name of Sponsor/Company: Innate Therapeutics Limited

Name of Product: MIS416

level using descriptive statistics.

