4.1 Overview of Study Design

This is a single center, open-label, non-randomized, dose-escalation study, to be conducted in two phases: a dose-escalation (DE) phase, to evaluate the safety, tolerability, MTD, and PD of MIS416 administered IV once weekly for 4 doses; and a dose-confirmation (DC) phase, which will be a cohort expansion at or below the MTD (i.e., the RP2D) of MIS416, dosed once weekly for up to 12 doses.

Subjects will be treated with a weekly IV dose of MIS416 in 28-day cycles: 1 cycle in the DE phase, and up to 3 cycles in the DC phase. The initial dose of MIS416 will be 125 μ g/week. Subjects will be evaluated and dosed weekly each cycle in each phase. Subjects will return for a follow-up visit 15 days after completion of the last dose of study drug.

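### Adverse-event percentages by dose cohort do not separate the 4-infusion escalation phase from the up-to-12-infusion confirmation phase, so the figure at the recommended dose can differ through exposure alone

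*Protocol*

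**What the plan says.** Section 14.5.3.2 fixes the main adverse-event summary: "The overall incidence of adverse events will be tabulated by dose cohort and total population". The measure is the number and percentage of subjects with at least one adverse event, serious event or treatment-related event. It adds: "If there are multiple occurrences of the same AE for the same subject, only the first occurrence will be counted". Section 14.4.1 sets the same layout generally: "For all subjects, the data will be tabulated by dose cohort and for the total patient population". The synopsis (Statistical Analysis, Safety Analyses) uses a slightly different grouping term: "The number and percentage of subjects experiencing one or more AEs will be summarized by dose level group". None of the three mentions phase, cycle or exposure as a stratum or denominator.

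Exposure differs by design. Section 4.1 plans "1 cycle in the DE phase, and up to 3 cycles in the DC phase". The DE phase is "administered IV once weekly for 4 doses" and the DC phase is "dosed once weekly for up to 12 doses". Section 4.5 recruits up to 15 DC subjects, all at the RP2D. Section 4.3 uses DE cohorts of 3, or 6 after one dose-limiting toxicity (DLT).

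Exposure is summarised in section 14.5.3.1: "Summary statistics will be presented for the number of infusions and the cumulative drug dose received by subjects in each dose cohort". A per-subject listing of infusions at each dose level is also planned there. Neither is linked to the adverse-event tables.

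**The concern.** The percentage of subjects who ever had an event rises with the number of infusions and the time at risk. Here only one dose level contains subjects with up to three times the planned exposure of everyone else. A reader who looks across the dose columns for a dose-toxicity pattern may be looking at duration instead. If the RP2D is the top dose tested, exposure can create or exaggerate a dose trend. If it is a middle dose, exposure can make it look worse than the doses above it.

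The trial tests no hypotheses (section 14.4.2), so these descriptive tables are its safety result, and section 2.3 intends them to support longer exposure in a larger trial. Section 7 also lists the timing of adverse events among the things to be characterised. A single ever/never percentage cannot separate events that first appear in Cycles 2 and 3 from those in the first four doses.

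**Working it through.** **Figures in the protocol.** The protocol gives no expected adverse-event rate, so there is no stated figure of this kind to reproduce. Its enrolment range is consistent: 12 + 15 = 27 and 18 + 15 = 33. Its escalation probabilities in section 14.1 also reproduce. For example, at a DLT rate of 30%, 0.7³ + 3 × 0.3 × 0.7² × 0.7³ = 0.343 + 0.441 × 0.343 = 0.494, against the stated 49%. That table concerns DLTs in the escalation phase and does not bear on this point.

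**Inputs.** Planned infusions are 4 (DE) and at most 12 (DC), from section 4.1. Subjects at the RP2D are 3 or 6 from DE (section 4.3) and up to 15 from DC (section 4.5). The per-infusion risk h of a given event is not in the documents. It is assumed constant, independent between infusions and equal at every dose (no dose effect), and is varied from 2% to 50%.

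**Formula.** Expected share of subjects with at least one event after k infusions: 1 − (1 − h)^k.

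| h | 4 infusions | 12 infusions | Ratio |
|---|---|---|---|
| 2% | 1 − 0.98⁴ = 7.8% | 1 − 0.98¹² = 21.5% | 2.8 |
| 5% | 1 − 0.95⁴ = 18.5% | 1 − 0.95¹² = 46.0% | 2.5 |
| 10% | 1 − 0.90⁴ = 34.4% | 1 − 0.90¹² = 71.8% | 2.1 |
| 20% | 1 − 0.80⁴ = 59.0% | 1 − 0.80¹² = 93.1% | 1.6 |
| 50% | 1 − 0.50⁴ = 93.8% | 1 − 0.50¹² = 99.98% | 1.07 |

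**If DE and DC subjects share the RP2D column (h = 5%).** With 3 DE and 15 DC subjects: (3 × 18.5 + 15 × 46.0) / 18 = 41.4%. With 6 DE and 15 DC subjects: (6 × 18.5 + 15 × 46.0) / 21 = 38.1%. Every other dose column has an expected value of 18.5%.

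**Total column (h = 5%, 12 DE and 15 DC).** (12 × 18.5 + 15 × 46.0) / 27 = 33.8%, a mixture of two exposure lengths. DC subjects make up between 15/33 = 45% and 15/27 = 56% of the total if all 15 are enrolled.

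**If DC subjects stop early.** Twelve is a maximum. At 8 infusions and h = 5%, 1 − 0.95⁸ = 33.7%, still well above 18.5%.

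**With the comparison limited to the first four infusions.** Every column, including DC, has the same expected value, 18.5% at h = 5%, as it should when dose has no effect.

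**The case against.** The strongest reply is that table layout belongs in the statistical analysis plan, which is not at hand, and that section 14.5.3.2 does not rule out further displays. That holds for detail the protocol leaves open. It does not remove the point, because the protocol does state a display in three places, and that display, followed as written, mixes dose with duration.

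Second, dose cohort may already mean a separate column for the DC expansion. Sections 4.1 and 4.8 can be read that way, and section 14.4.1 mentions a further safety summary for an MTD population. This stands: pooling is one reading, not a stated rule, and the 41.4% applies only under it. With a separate column the DE cohorts stay comparable with each other at equal planned exposure. If the RP2D is a tested DE level, its own DE subjects belong to that comparison. A reader might therefore infer that dose and exposure are wholly confounded, but the documents do not support that. What remains is the comparison of the DC column with the DE columns, which is unequal under either reading.

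Third, the exposure table, the infusion listing and the adverse-event listings would let someone recover part of the picture in a trial of 27 to 33 subjects. That is also true, so it would go too far to say that the problem cannot be corrected. The summary tables alone do not correct it, however.

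Fourth, fever and chills are the response the sponsor looks for (sections 1.4.5 and 2.1), so the percentage with any adverse event may be near 100% in every column. The 50% row of the table confirms that the gap then almost disappears.

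**Conclusion.** The point holds for the descriptive safety profile by dose. Under a constant, equal per-infusion risk, going from 4 to 12 infusions multiplies the expected percentage by 2.1 to 2.8 at risks of 2% to 10%, by 1.6 at 20%, and by 1.07 at 50%. It therefore matters for infrequent or cumulative events, including serious ones, and little for near-universal infusion reactions. These are expected values. A cohort of 3 can only show 0, 33, 67 or 100%.

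Two stronger readings are tempting and are not supported. One is that the RP2D will necessarily look more toxic. Antipyretic pre-medication (section 4.7) and dose reduction (section 4.6) are provided for in the DC phase only, and DC entry is limited to secondary progressive disease (section 5.2). Any of these may shift DC rates, so the net direction is uncertain. They are further reasons to keep the phases apart. The other is that dose selection is compromised. DLTs are counted in the DE phase only (section 4.4), and the dose for the DC phase is set before any DC data exist (sections 4.3 and 4.8). The MTD and RP2D decisions are not affected.

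**What to change.** In section 14.5.3.2, with the synopsis and section 14.4.1 brought into line:

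1. Show DE and DC subjects in separate columns, even at the same dose, and use one defined term in place of both dose cohort and dose level group.
2. Base any comparison across dose levels on adverse events from Cycle 1 (the first four infusions) in all subjects, including DC.
3. For the DC phase, also report adverse events by cycle or per infusion received, taking the infusion counts from section 14.5.3.1. A per-infusion rate needs all occurrences counted, so the first-occurrence rule should be confined to the percentage tables.
4. Keep the total column, which is conventional, and add a footnote giving the unequal exposure of its two parts.

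The cost is revised wording and a few extra tables. No new data are needed, and trial conduct does not change.

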12.2.6 Causality Assessment

The Investigator's assessment of causality must be provided for all AEs (serious and nonserious). An investigator's causality assessment is the determination of whether there exists a reasonable possibility that the investigational product caused or contributed to an AE. For this assessment, investigators must categorize the causality as unrelated, possibly related, probably related or related according to the following definitions:

Unrelated: There is evidence that the AE definitely has an etiology other than the assigned study drug.

Version 5

- **Possibly Related:** The adverse event has a temporal relationship to study drug administration. However, an alternative etiology may be responsible for the AE. Information on drug/product withdrawal may be lacking or unclear.
- **Probably Related:** The AE has a temporal relationship to study drug administration. The event is unlikely to be related to an alternative etiology. There is a reasonable response on withdrawal (dechallenge).
- **Related:** The adverse event has a temporal relationship to study drug administration and resolves when the drug is discontinued. An alternative etiology is not apparent.

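### Counting only a subject's first occurrence of an AE can understate grade and attribution in the safety tables, and the category *related* has no cell

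*Protocol*

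**What the plan says.** Protocol section 14.5.3.2 announces a severity table: "The incidence of adverse events by intensity/grade (Grades 1, 2, 3, and 4"). It also announces a table "by relationship to study drug (not related, possibly related, and probably related"). Shortly afterwards it gives the only counting rule for repeated events: "If there are multiple occurrences of the same AE for the same subject, only the first occurrence will be counted". No rule based on the maximum grade or the strongest relationship appears anywhere in the protocol.

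On causality, section 12.2.6 says that "investigators must categorize the causality as unrelated, possibly related, probably related or related according to the following definitions". The top level, *related*, has its own definition, which includes the condition "An alternative etiology is not apparent". Section 14.5.3.2 itself defers to the protocol for "The categories and definitions of severity and causal relationship for all AEs".

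Section 7 makes the safety profile, together with the MTD, the primary endpoint. It names severity and relationship to treatment among the features of AEs to be characterised.

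**The concern.** Dosing is weekly, with 4 doses in the dose-escalation (DE) phase and up to 12 in the dose-confirmation (DC) phase (section 4.1), so the same preferred term can recur in one subject. The protocol expects flu-like reactions, fever and chills above all (sections 1.4.5 and 2.1). Section 4.7 lets DC subjects carry on at an unchanged dose after pyrexia or rigors/chills up to Grade 3. A rule that keeps only the first episode discards the grade and attribution of every later one.

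What is at stake is the severity and relationship part of the safety profile. The DC phase is meant to build a safety base for longer exposure (section 2.3), and later episodes are the information that longer exposure adds. In the relationship table, an event placed in the strongest category has nowhere to go. The programmer would have to drop it, merge it or add a column without instruction.

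**Working it through.** **Step 1: the counting rule, read literally.** A subject has fever of Grade 1 after one infusion and fever of Grade 3 after a later one. Both carry the same preferred term. Only the first counts, so the subject falls under Grade 1. In the same way, an event first judged unrelated and later judged related falls under not related. A first occurrence can never exceed the maximum over all occurrences. Compared with a worst-grade or strongest-relationship table, the error therefore has one direction. There is no error when the first episode is also the worst.

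**Step 2: the categories side by side.**

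| Section 12.2.6 (collected) | Section 14.5.3.2 (tabulated) |
|---|---|
| Unrelated | Not related |
| Possibly related | Possibly related |
| Probably related | Probably related |
| Related | no cell |

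Four levels are collected and three tabulated, although section 14.5.3.2 says that the protocol's categories apply. *Treatment-related*, used in the overall incidence table, is not mapped to the four levels.

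**Step 3: size, as illustration only.** The protocol states no figure that depends on this rule, so there is nothing to reproduce. It also gives no rate of Grade 3 or higher per episode. Assume:

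- g = chance that an episode is Grade 3 or higher, independent between episodes (assumed range 5% to 30%);
- k = number of doses, 4 or 12 (section 4.1);
- the event recurs at every dose.

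The first-occurrence table shows g. A worst-grade table shows 1 − (1 − g)^k. The share of affected subjects missed is 1 − g / [1 − (1 − g)^k].

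| g | Shown | Worst grade, k = 4 | Missed | Worst grade, k = 12 | Missed |
|---|---|---|---|---|---|
| 5% | 5% | 18.5% | 73% | 46.0% | 89% |
| 10% | 10% | 34.4% | 71% | 71.8% | 86% |
| 20% | 20% | 59.0% | 66% | 93.1% | 79% |
| 30% | 30% | 76.0% | 61% | 98.6% | 70% |

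For g = 10%: 1 − 0.9^4 = 0.344 and 1 − 0.9^12 = 0.718. Among 15 DC subjects receiving all 12 doses this is 15 × 0.10 = 1.5 shown, against 15 × 0.718 = 10.8.

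**Step 4: a milder assumption.** Let the event occur at each dose with probability r. The table then shows [1 − (1 − r)^k] × g, and a worst-grade table shows 1 − (1 − r × g)^k. For r = 30%, g = 10% and k = 4 this is (1 − 0.7^4) × 0.10 = 7.6% against 1 − 0.97^4 = 11.5%, so 34% of affected subjects are missed. Over r = 30% or 60% and g = 10% or 20%, the share missed is 31% to 56% for 4 doses and 62% to 81% for 12.

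**The case against.** The strongest reply is that much of the safety result does not pass through these two tables, and that stands. The MTD rests on dose-limiting toxicities and the Safety Review Team (sections 4.3, 4.8 and 11.2). The overall table still counts subjects with at least one AE, serious AE or treatment-related AE, along with deaths and discontinuations. The listings keep the events and flag DLTs. Temperature is a vital sign and is summarised at each timepoint (sections 7.5 and 14.5.3.4). None of this restores the severity table, however. The overall rows carry no grade, DLTs apply to the DE phase only, and Grade 3 fever and rigors/chills are excepted from them (section 4.4).

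A second reply is that the percentages have no basis in the documents, and this too stands. The human experience cited is of Grade 1 to 2 symptoms described as an initial response. Antipyretic premedication (section 4.7) and dose reduction (section 4.6) in the DC phase work against independent, equally severe episodes. In the DE phase most other related Grade 3 or 4 events are DLTs and lead to withdrawal, so the loss there would mainly concern fever and chills.

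A third reply is that the three-level list is a slip, since the same section defers to the protocol's categories. It probably is, but as written the section contradicts itself.

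A reader might also infer that DE and DC subjects are mixed within each dose column, which would confound dose with number of infusions. The documents do not establish this. Section 14.4.1 says: "For all subjects, the data will be tabulated by dose cohort and for the total patient population". Sections 4.1 and 4.8 treat the DC phase as a cohort of its own. Only the total column certainly pools the phases, and section 14.5.3.1 reports infusions and cumulative dose by cohort.

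**Conclusion.** The point holds for the by-grade and by-relationship tables. The rule as stated understates severity or attribution whenever a later occurrence is worse or more strongly attributed than the first, and it never overstates them. That is plausible for fever and chills under up to 12 weekly doses. Separately, the relationship table lacks one of the four levels that section 12.2.6 requires, contrary to the section's own cross-reference.

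The size cannot be derived from the documents. The contrast of 10% with 34% or 72% assumes recurrence at every dose and independent grades. It is smaller with less frequent recurrence, or if reactions lessen with repeated dosing, and it should not be cited as an expected effect. It would also go too far to say that the primary safety result as a whole is wrong, or that *related* events are deleted. The protocol does not say what happens to them, and the MTD, the serious-event, death and discontinuation counts and the listings do not depend on this rule.

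**What to change.** In section 14.5.3.2, replace the first-occurrence sentence with: *each subject is counted once per preferred term at the maximum grade and, separately, at the strongest relationship, over all occurrences*. List the four relationship categories of section 12.2.6 in place of the three, and define treatment-related as possibly related, probably related or related.

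The cost is protocol wording, matching wording in any analysis plan, and table shells. No new data are needed. The downside is that the severity figures may look less favourable than under the present rule. The change should be made before the tables are produced.
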